### 7.12 **Prior & Concomitant Therapy**

Treatments that have been administered within the 7 days prior to the date of informed consent, or during the Screening phase, will be recorded in the eCRF. The investigator is to instruct the subject to notify the study site about any new medications he/she takes after the start of the test article. All medications and significant non-drug therapies (including physical therapy and blood transfusions) administered after the subject starts treatment with test article must be listed in the eCRF (see Section 10). In addition, for antibacterial agents administered, the dose, unit, frequency and route must be entered in the eCRF.

### 7.13 **Prohibited Therapy**

All investigational medications or devices used during the 30 days prior to Screening are prohibited.

All of the following therapies are excluded starting from the time of consent through EOT visit:

- More than 1 dose of a potentially therapeutic antibacterial agents (with potential activity against pathogens responsible for CABP) are prohibited for 72 hours prior to randomization through EOT, with the exception of cases where a subject is deemed a clinical failure during the course of the study and requires treatment with an additional antibacterial agent
- Subjects will be instructed to avoid taking antacids and multivitamins containing multivalent cations (eg, aluminum, magnesium, calcium, bismuth, iron, or zinc) for 4 hours before and within 4 hours after oral doses

#### 7.13.1 Concomitant Medications That May Interact With Moxifloxacin

Use of proarrhythmic or QT prolonging medications is prohibited through the EOT. After EOT through Final Follow-up, the investigator should use clinical judgement regarding the use of such medications, given the half-life of moxifloxacin. For other warnings, precautions, and drug interactions for moxifloxacin please see the most current version of the moxifloxacin full prescribing information provided under separate cover.

## 7.14 Permitted Treatments

All other treatments not specified as prohibited are permitted during the study. Subjects requiring additional or alternative antibacterial therapy for their CABP will be judged as Clinical Failures and test article will be discontinued. Further treatment for their infection is at the discretion of the investigator or the subject's health care provider and will be considered as a concomitant medication.

Subjects should be encouraged to contact site personnel before starting any new treatment.

For all treatments received by the subject during the study, relevant information must be recorded on the subject's eCRF.

#### 7.15 Treatment Compliance

Intravenous and oral administration will be managed by study personnel. Compliance and any unresolved discrepancies will be documented in the source document and on the drug inventory record. The test article eCRF should reflect the reconciled dosing information provided by the subject charts.

### 7.16 Packaging and Labeling

The investigational test article, omadacycline and moxifloxacin will be packaged by the sponsor and supplied to the investigator. Please refer to the Pharmacy Manual for additional information.

### 7.17 Storage and Accountability

Test article must be received at the study site by a designated person, acknowledged in the IxRS, handled and stored safely and properly, and kept in a secured location to which only the investigator and designated staff have access. Upon receipt, the test article should be stored according to the instructions specified on the drug labels. Storage conditions must be adequately monitored, and appropriate temperature logs maintained as source data.

The designated study personnel must maintain an accurate record of the shipment and dispensing of test articles in the study specific medication accountability ledger. Intravenous drug accountability will be performed by unblinded personnel. Oral drug accountability can be performed by blinded or unblinded personnel.

### 7.18 Investigational Product Retention at Study Site

At the conclusion of the study, and as appropriate during the course of the study, with instruction from the sponsor, the designated study personnel will destroy on site as permitted by local site operating procedures, or return all unused test articles, packaging, and drug labels. Destruction/return of all test article will be documented and maintained in the site files.

# 8 STUDY PROCEDURES

Written, signed, and dated informed consent will be obtained before any study-related procedures have been performed. Upon signing the informed consent, the subject will then be assigned a study subject number. Adverse events must be recorded from the time the ICF is signed. Subjects who have been pre-screened on the telephone but who do not sign an ICF will not be assigned a subject number. The investigator will maintain a subject master list to document every subject who has signed an ICF. A copy of this list should be retained in the investigator's study files.

### 8.1 Informed Consent

The investigator will provide for the protection of the subjects by following all applicable regulations. These regulations are available upon request from the sponsor. The ICF must be reviewed by the sponsor and approved by the IRB/IEC/REB.

Before any procedures specified in the protocol are performed, a subject must:

- Be informed of all pertinent aspects of the study and all elements of informed consent
- Be given time to ask questions and time to consider the decision to participate
- Voluntarily agree to participate in the study
- Sign and date an IRB/IEC/REB approved ICF

#### 8.2 Subject Demographics/Other Baseline Characteristics

Subject demographic and baseline characteristic data to be collected on all subjects include: date of birth (per local regulations), gender, and race/ethnicity.

#### 8.3 Medical History

The investigator will perform a comprehensive history at the Screening visit. Significant medical history (at any time) and any medical history within the past 6 months including ongoing medical conditions at the time of signing of the ICF will be recorded. In addition, subject's history of prior CABP will be captured and the following:

- Predisposing factors that may affect lung function (eg, prior lung infection, mild to moderate COPD, symptomatic asthma with wheezing, history of smoking, chronic cough with and without sputum production, etc).
- Cardiovascular disease and risk factors
- History of pneumococcal vaccination (eg, Pneumovax, Prevnar 13).
- All systemic antimicrobials from onset of the infection will be recorded under concomitant medications.

Where possible, diagnoses are to be recorded. Any event or change in the subject's condition or health status occurring after signing the ICF will be reported as an AE.

## 8.4 Physical Examination

At Screening, a full physical examination will include the examination of general appearance, skin, neck (including thyroid), eyes, ears, nose, throat, lungs, heart, abdomen, back, lymph nodes, extremities, and vascular and neurological systems. Beyond the Screening visit, abbreviated physical examinations may be performed (see Appendix 1).

Information for all physical examinations must be included in the source documentation at the study site. Significant and relevant findings that are present prior to the signing of the ICF must be included in the subject's eCRF. Relevant findings that are present prior to the signing of the ICF must be included in the relevant medical history/current medical conditions screen on the subject's eCRF. New clinically significant findings made after the signing of the ICF which meet the definition of an AE must be recorded as an AE in the subject's eCRF.

#### 8.5 Vital Signs

Vital signs including BP, heart rate, respiratory rate, pulse oximetry and body temperature will be measured at the timepoints as specified in Appendix 1. Additionally, BP and heart rate should be measured within 30 minutes before, and approximately 1 hour ( $\pm$  15 minutes) after the completion of the infusions on Day 1 and Day 2.

The subject's BP and heart rate should be captured after at least 5 minutes (+ 5 minutes) of rest while in a non-standing position (supine or semi-recumbent, head of bed from  $0^{\circ}$  to  $90^{\circ}$ ). Subsequent vital sign measurements should be captured in the same non-standing position.

Systolic and diastolic BP will be measured using an automated calibrated device, with an appropriately sized cuff.

Heart rate will be measured using an automated calibrated device, when available. If not available, heart rate will be measured manually.

Temperature will be obtained using an electronic (rapid reading) device whenever possible and the same device should be used for all study assessements.

#### 8.6 Electrocardiogram

A standard 12-lead ECG should be obtained using site equipment. The ECG will be obtained after the subject has been in a semi-recumbent position for approximately 10 minutes at the following times:

- Screening-any time during the visit
- EOT-any time during the visit
- In any case in which a subject develops an AE of non-pleuritic cardiac chest pain, palpitations, tachyarrhythmia, or as otherwise clinically indicated
- Additional ECGs can be performed as needed at the discretion of the investigator.

Reading and interpretation of the ECG will be performed locally and reviewed by the investigator for interpretation, and hard copies of the reports retained in the files.

### 8.7 Height and Weight

Height and body weight will be collected and recorded in the eCRF.

#### 8.8 Assessment of CABP Symptom Severity

The investigator will specifically assess the presence and severity level of the subject's symptoms of cough, sputum production, pleuritic chest pain and dyspnea on a 4-point scale (absent, mild, moderate, or severe) based upon the Community-Acquired Bacterial Pneumonia Subject Symptom Severity Guidance Framework for Investigator Assessment (see Appendix 3) and enter the symptom severity level into the eCRF. Subjects must have at least 3 of these 4 symptoms of CABP to be eligible for randomization in the study.

### 8.9 Radiologic Evaluation of Pneumonia

A CXR or CT scan will be obtained for all subjects at Screening (within 48 hours prior to the first dose of test article, see Inclusion Criteria 7). These studies may be obtained as part of routine, non-study evaluation of a subject presenting with signs and symptoms of CABP and therefore may be performed in some circumstances before informed consent is obtained for participation in this study. If a CXR or CT scan is obtained during the course of therapy or during the period up to the Final Follow-up assessment, the results of the study will be collected. Radiologic evaluation(s) will be performed locally and interpreted by appropriately qualified personnel who are certified or licensed to interpret chest radiographs according to applicable regional requirements, reviewed by the investigator or qualified personnel and the conclusions of this review will be the basis for subject inclusion. The review report should be included in the source documents.

### 8.10 PORT Risk Class

All subjects who are being screened for the study will have their PORT Risk Class assessed at the Screening evaluation only (see Appendix 5). As part of the Inclusion Criteria to this study, all subjects must have disease characterized as PORT Risk Class of III or IV at randomization and randomization will be stratified by PORT Risk Class to ensure balance between treatment arms.

# 8.11 SF-36v2® Health Survey

At the Screening and Final Follow-up visits, the subject will complete a SF- $36v2^{\text{(B)}}$  Health Survey (Medical Outcomes Trust, OptumTM). The SF- $36v2^{\text{(B)}}$  Health Survey asks 36 questions to measure functional health and well-being from the subject's point of view. It is a practical, reliable and valid measure of physical and mental health that can be completed in five to ten minutes. It is referred to as a generic health survey because it can be used across age (18 and older), disease, and treatment group, as opposed to a disease-specific health survey, which focuses on a particular condition or disease.

## 8.12 Clinical Laboratory Tests

Clinical safety laboratory tests to be performed include hematology, prothrombin time (international normalized ratio), serum chemistry, and pregnancy tests (urine or serum). The Central Laboratory will be used for safety analysis of all specimens collected. Details on the collection tubes and containers, shipment of samples and reporting of results by the Central Laboratory are provided to investigators in the Central Laboratory Manual.

Because subject enrollment will not permit using Central Laboratory results to assess a subject's eligibility, it is expected that local laboratory testing will be used in circumstances where this testing is needed..

#### 8.12.1 Central Laboratory Parameters

Clinical laboratory tests will include the following:

#### **Clinical Laboratory Tests (Central)**

Hematology:		Serum Chemistry:	
•	Hematocrit (Hct)	• Alkaline phosphatase (ALP)	
•	Hemoglobin (Hgb)	• Alanine aminotransferase (ALT)	
•	Mean corpuscular hemoglobin (MCH)	• Aspartate aminotransferase (AST)	
•	Mean corpuscular hemoglobin	• Blood urea nitrogen (BUN)	
	concentration (MCHC)	• Calcium (Ca)	
•	Mean corpuscular volume (MCV)	• Carbon dioxide (CO 2 )	
•	Platelet count	• Chloride (Cl)	
٠	Red blood cell (RBC) count	Creatinine	
•	White blood cell (WBC) count with differential	• Creatine phosphokinase (CK)	
		• Gamma-glutamyl transpeptidase (GGT)	
Coagulation:		• Lipase	
•	Prothrombin time international normalized	Magnesium	
ration (INR)		Phosphorus (P)	
Pregnancy (all female subjects):		• Potassium (K)	
•	Serum $\beta$ -human chorionic gonadotropin ( $\beta$ -HCG)	• Sodium (Na)	
		Total bilirubin	

In addition, blood samples will be collected and sent to the Central Laboratory for serologic microbiology testing (Section 8.12.2.2).

#### 8.12.2 Local Laboratory Parameters

#### 8.12.2.1 Pregnancy Assessments

All subjects will have a local urine or serum pregnancy test at the site at the Screening. Urine pregnancy test kits will be provided by the sponsor through the Central Laboratory. If a positive urine or serum pregnancy test result is obtained at the site during Screening, the subject is not to be randomized. A serum sample for serum  $\beta$ -human chorionic gonadotropin ( $\beta$ -hCG) testing will

be collected at the Screening visit and sent to the Central Laboratory for confirmation of the local urine or serum pregnancy test results as well as at EOT and PTE. If a positive  $\beta$ -hCG result is reported by the Central Laboratory after a subject is enrolled, test article administration should be discontinued (see Section 8.22).

#### 8.12.2.2 Blood Cultures

Two sets of blood cultures (1 set = 1 aerobic bottle + 1 anaerobic bottle) should be collected within the 24 hours prior to the first dose of test article. Each set of blood cultures should be collected by direct venipuncture from independent body sites at least 15 minutes apart. If bacteria are isolated from baseline blood cultures, repeat blood cultures must be collected on the day that the positive blood culture is detected. If subsequent blood cultures are also positive, repeat the blood cultures as necessary until negative blood cultures are obtained. Blood culture isolates should be sent to the Central Laboratory.

#### 8.12.2.3 Sputum and Urine Samples

Samples of sputum and urine will be collected and sent to the local laboratory for microbiology testing (Section 8.14.1).

#### 8.12.2.4 SARS-CoV-2 Sample

In addition to any local SOC assessment of SARS-CoV-2, molecular testing for SARS-CoV-2 will be performed at the local laboratory (or a regional reference laboratory) using an upper respiratory sample (e.g. nasopharyngeal swab or saliva) collected at Screening. Test results from this sample are not required before a subject is randomized. However, test results will be documented in the database. If a positive test result is obtained after randomization, the investigator will determine whether a subject should continue study treatment (see Section 7.6.4). Repeat testing may be completed as clinically indicated and should be recorded. Please see laboratory manual for additional testing information.

#### 8.12.3 Blood Volume

The total volume of blood collected from each subject will be approximately 4 to 15 mL per visit, or approximately 51 mL (approximately 3.5 tablespoons) over the course of the study. In addition, a blood culture will be collected at Screening and repeated if positive. The preferred volume for each blood culture bottle is 10 mL. However, since these are analyzed locally, site staff should refer to their individual laboratory or manufacturers' recommendation.

#### 8.13 Efficacy Assessments

#### 8.13.1 Investigator's Assessment of Clinical Response

In order to satisfy different health authority requirements, the primary variables assessing efficacy will be tested with 2 response endpoints.

# 8.13.1.1 Evaluation of the Infection Under Study at the Early Clinical Response Assessment

The formal determination of the response to therapy at the ECR assessment (72 to 120 hours after administration of the first dose of test article) will be done programmatically using the investigator's assessment of the subject's symptoms associated with CABP entered into the eCRF. The investigator is not responsible for categorizing subjects as Clinical Success, Failure, or Indeterminate at the ECR assessment. The severity of the subject CABP symptoms of cough, sputum production, pleuritic chest pain and dyspnea will be evaluated on a 4-point scale (absent, mild, moderate, or severe) based upon the Community-Acquired Bacterial Pneumonia Subject Symptom Severity Guidance Framework for Investigator Assessment (see Appendix 3). A CABP subject symptom severity assessment should be completed at every scheduled evaluation with the exception of the Final Follow-up assessment (see Section 8.8 and Appendix 1). For subjects that have been switched to po test article and discharged from the hospital prior to Study Day 4, only 1 visit is required between Study Days 4 to 6 (see Appendix 1 for ECR study procedures). Subjects who remain hospitalized during the ECR phase should have the study procedures performed each day (see Appendix 1).

Clinical Success: at the ECR assessment will be defined as survival with improvement of at least 1 level (ie, severe to moderate, moderate to mild, mild to absent) compared to Screening in 2 of the 4 CABP symptoms (cough, sputum production, pleuritic chest pain, and dyspnea) with no worsening by at least 1 level in the other inclusion CABP symptoms. In order for the subject to be considered a Clinical Success, the subject may not meet any criteria for Clinical Failure or Indeterminate ECR.

Clinical Failure: defined as meeting any of the following criteria:

- There is no improvement by at least 1 level (ie, severe to moderate, moderate to mild, mild to absent) compared to Screening in 2 CABP symptoms.
- Any of the 4 CABP symptoms is worse (by at least 1 level) compared to Screening.
- The subject requires alternative (rescue) antibacterial treatment for CABP prior to the ECR assessment related to either (a) progression or development of new symptoms attributable to CABP or (b) development of infectious complications of CABP (eg, empyema, lung abscess).
- The subject is receiving antibacterial therapy that may be effective for the infection under study for a different infection from the one under study.
- Discontinued study therapy due to an AE and received alternative antibacterial treatment for CABP prior to the ECR assessment.
- Death prior to the ECR assessment.

Indeterminate: the clinical response to test article could not be adequately inferred due to:

• Subject was not seen for the evaluation because they withdrew consent or were lost to follow-up.

• Other specified reason.

#### 8.13.1.2 Investigator's Assessment of Clinical Response at EOT

End of treatment assessments should be performed on the calendar day of, or within 2 days following the last dose of any test article. If a subject withdraws prematurely or terminates participation in the study prior to completion of the planned antibiotic therapy, the EOT visit should be conducted.

The investigator will determine which of the following clinical outcomes the subject meets based on the criteria below (must select 1 outcome):

#### Clinical Success:

- The subject is alive and the infection is sufficiently resolved such that further antibacterial therapy is not needed.
  - These subjects may have some residual findings related to infection (ie, cough) requiring ancillary (ie, non-antibiotic) treatment (eg, expectorant).
- In order for the subject to be considered a Clinical Success at EOT, the subject may not meet any criteria for Clinical Failure or Indeterminate at EOT.

#### Clinical Failure:

- The subject requires alternative antibacterial treatment for CABP prior to EOT related to either:
  - a. progression or development of new symptoms of CABP or,
  - b. development of infectious complications of CABP (eg, empyema, lung abscess) or,
  - c. subject developed an AE that required discontinuation of study therapy.
- Other reasons for Clinical Failure are:
  - d. Subject is receiving antibacterial therapy that may be effective for the infection under study for a different infection from the one under study.
  - e. Death prior to EOT visit.

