5.2.2 Secondary Efficacy Outcomes

5.2.2.1 Investigators Assessment of Clinical Response

The investigator will make an assessment of Clinical Response at the EOT and PTE Visits, based on the definitions below. The secondary efficacy outcome is clinical response at PTE based on the investigator assessments at the EOT and PTE Visits in the ITT and CE-PTE populations as defined in Table .

EOT Visit

At the EOT Visit (on the calendar day of, or within 2 days following the last dose of test article), the investigator will indicate the clinical status of the infection under study as detailed below.

Clinical Success:

- The subject is alive and the infection is sufficiently resolved such that further antibacterial therapy is not needed.
 - These subjects may have some residual findings related to infection (ie, cough) requiring ancillary (ie, non-antibiotic) treatment (eg, expectorant).
- In order for the subject to be considered a Clinical Success at EOT, the subject may not meet any criteria for Clinical Failure or Indeterminate at EOT.

Clinical Failure:

- The subject requires alternative antibacterial treatment for CABP prior to EOT related to either
 - progression or development of new symptoms to CABP, or
 - development of infectious complications of CABP (eg, empyema, lung abscess), or
 - \circ subject developed an AE that required discontinuation of study therapy prior to the EOT.

Other reasons for clinical failure are:

- Subject is receiving antibacterial therapy that may be effective for the infection under study for a different infection from the one under study.
- Death prior to EOT.

Indeterminate:

- The clinical response to test article could not be adequately inferred due to:
 - Subjects were not seen for EOT evaluation because they withdrew consent, were lost to follow-up, other reason (specify).
 - Other specified reason.

PTE Visit

At the PTE Visit (5 to 10 days after the subject's last day of study therapy) the investigator will indicate one of the following outcomes relating to the primary infection under study:

Clinical Success:

- Survival after completion of a test article regimen without receiving any systemic antibacterial therapy other than test article;
- Resolution of signs and symptoms of the infection present at Screening with no new symptoms or complications attributable to CABP; and
- No need for further antibacterial therapy.

Clinical Failure:

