6.1.4.4 Test Article Therapy

Subjects must meet all of the following to be included in the CE populations:

- Received at least 1 dose of active test article and the correct test article based on the randomization assignment.
- Study personnel involved in the assessment of efficacy remained blinded to study treatment, unless a treatment limiting adverse event (AE) occurred which required emergency unblinding.
- Evaluable failure: The subject received the first 2 doses (if receiving 200 mg iv QD on Day 1) or 3 doses (if receiving 100 mg iv on Day 1) of active test article (omadacycline group) or first 2 doses of active test article (moxifloxacin group) and the investigator classifies the subject as a Clinical Failure at the EOT Visit (CE-EOT population) or the overall Clinical Response (based on the investigator's assessment) at the PTE Visit (CE-PTE population) is Clinical Failure.
- Evaluable success: The subject received the first 3 doses (if receiving 200 mg iv QD on Day 1) or 4 doses (if receiving 100 mg iv on Day 1) of active test article (omadacycline group) or the first 3 doses of active test article (moxifloxacin group) and the investigator classifies the subject as a Clinical Success at the EOT Visit (CE-EOT population) or the overall Clinical Response (based on the investigator's assessment) at the PTE Visit (CE-PTE population) is Clinical Success.

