6.1.4.5 Clinical Outcome Assessment

Subjects must meet the following to be included in the CE populations:

- For the CE-EOT population:
 - Completed the investigator's assessment of clinical response (ie, was not deemed an indeterminate outcome) at the EOT Visit, and
 - The EOT Visit occurred on the day of, or within 2 days following the last dose of test article.
- For the CE-PTE population:
 - The overall Clinical Response (based on the investigator's assessment) at the PTE Visit is not Indeterminate.
 - The PTE Visit occurred 5 to 10 days after the last dose of test article, unless the subject was considered to be a Clinical Failure based on the investigator's assessment at the EOT Visit or the patient died after EOT and before PTE.

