6.1.5 Microbiologically Evaluable (ME) Populations

The ME-EOT and ME-PTE populations will consist of all subjects in both the microITT and the CE-EOT and CE-PTE populations, respectively.

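### CE-EOT requires a timely EOT Visit with no exception for death, so read literally it can drop deaths that the plan scores as EOT failures

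*Protocol*

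**What the plan says.** **Outcome definition.** Protocol 8.13.1.2 counts "Death prior to EOT visit" as a Clinical Failure at EOT. SAP 5.2.2.1 has the same reason, "Death prior to EOT". In both documents Indeterminate is kept for withdrawn consent, loss to follow-up or another specified reason.

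**CE-EOT membership.** SAP 6.1.4.5 opens with "Subjects must meet the following to be included in the CE populations". For CE-EOT it asks for a completed investigator assessment that is not Indeterminate, and adds: "The EOT Visit occurred on the day of, or within 2 days following the last dose of test article". No exception follows.

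**CE-PTE membership.** The corresponding bullet in the same section sets a window of 5 to 10 days after the last dose. It waives that window for a Clinical Failure assessed "at the EOT Visit or the patient died after EOT and before PTE".

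**Dosing rule.** SAP 6.1.4.4 has its own mandatory list ("Subjects must meet all of the following to be included in the CE populations"). An evaluable failure needs the first 2 doses, or 3 for omadacycline started at 100 mg. An evaluable success needs one dose more.

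**ME populations.** SAP 6.1.5: "The ME-EOT and ME-PTE populations will consist of all subjects in both the microITT and the CE-EOT and CE-PTE populations, respectively".

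**The concern.** The outcome definition and the population definition do not fit together. One says that a subject who dies before EOT has an outcome, and that it is failure. The other asks for a visit that such a subject may never have had. If the visit bullet is programmed as written, it removes these subjects because of their outcome. The loss runs one way: every subject dropped for this reason is a failure, so the success rate in CE-EOT can only rise, and it rises more in the arm with more such deaths.

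At stake are the analyses built on these populations in SAP 9.4 and Appendix 2: investigator-assessed response at EOT in CE-EOT and, in ME-EOT, clinical success by MIC and microbiological response by subject and by pathogen. The CE and ITT results at EOT would also treat the same deaths differently, which a reader of the study report would have to untangle.

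**Working it through.** **Step 1. Follow one subject through the rules.** Take a subject who receives the minimum doses for an evaluable failure, meets the other CE criteria, and dies on treatment before any EOT Visit.

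| Rule | Result |
|---|---|
| Protocol 8.13.1.2, SAP 5.2.2.1 | Clinical Failure at EOT; counted in the ITT analysis |
| SAP 6.1.4.4, evaluable-failure dosing | Met |
| SAP 6.1.4.5, CE-EOT, outcome not Indeterminate | Can be met, since death is a failure |
| SAP 6.1.4.5, CE-EOT, visit within 0 to 2 days of last dose | Not met if there was no visit; no exception |
| SAP 6.1.5, ME-EOT | Out, because CE-EOT is required |
| SAP 6.1.4.5, CE-PTE | The death exemption does not apply (it covers "or the patient died after EOT and before PTE"), but the exemption for an EOT Clinical Failure does if that failure was recorded; the failure then carries forward under SAP Table 4 |

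The visit-timing bullet alone decides the exclusion. The dosing rule in 6.1.4.4 is a further condition and does not waive the window. SAP 7.6 repeats that visits outside the window lead to exclusion from CE and ME and does not mention deaths.

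**Step 2. The plan's nearest figure.** The documents give none for CE-EOT. The only CE figures are for PTE: 670 × 0.80 = 536 subjects, or 268 per arm, with 89% success (SAP 5.1.1, protocol Table 4), margin 10% and one-sided alpha 0.025. The Farrington-Manning power is

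Φ[(0.10 − 1.96 σ₀) / σ₁]

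- σ₁ = √(2 × 0.89 × 0.11 / 268) = 0.02703.
- σ₀ uses the restricted estimates 0.8228 and 0.9228: √[(0.8228 × 0.1772 + 0.9228 × 0.0772) / 268] = 0.02846.
- Power = Φ(1.636) = 94.9%, as stated.

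This calculation concerns PTE and does not change.

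**Step 3. Illustrate the size at EOT.** Borrow n = 268 per arm and 89% success, so s = 239 and s/n = 89.2%. Let d be the number of deaths before an EOT Visit that meet every other CE criterion. Keeping them gives s/n; dropping them gives s/(n − d). The shift is s·d / [n(n − d)].

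| d (assumed) | Share of 268 | Rate with deaths dropped | Shift, points |
|---|---|---|---|
| 1 | 0.4% | 239/267 = 89.5% | +0.3 |
| 2 | 0.7% | 239/266 = 89.8% | +0.7 |
| 3 | 1.1% | 239/265 = 90.2% | +1.0 |
| 5 | 1.9% | 239/263 = 90.9% | +1.7 |
| 8 | 3.0% | 239/260 = 91.9% | +2.7 |

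**Step 4. Effect on the difference.** With 239/268 in both arms the difference is 0.0 when deaths are kept. After dropping them:

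- 2 against 0 deaths: 89.85 − 89.18 = 0.67 points.
- 5 against 2 deaths: 90.87 − 89.85 = 1.02 points.
- 8 against 4 deaths: 91.92 − 90.53 = 1.39 points.
- Equal deaths in both arms: 0.0.

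Each non-zero difference favours the arm with more deaths, whichever arm that is.

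**The case against.** The strongest reply is that the text does not show these deaths are in fact lost.

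- **An EOT outcome may exist for a subject who died.** The protocol tells the investigator to pick one EOT outcome, and death before EOT is one of the options. The route by which such a death reaches CE-PTE also presupposes an EOT assessment. With once-daily dosing, a death on treatment will usually fall within 2 days of the last dose, so an outcome dated at death would meet the timing. This stands as a way some cases could be kept. It depends on site practice, and no rule tells sites to do it.
- **The missing exception may be natural.** A death between EOT and PTE can easily precede a window that opens on day 5, whereas the EOT window opens at once. That may explain why only CE-PTE has a waiver. It does not supply the visit that CE-EOT asks for.
- **Manual review.** SAP 6.2.2 lets the Evaluability Review Team take part in deciding CE membership. That could retain a case, but a judgement case by case is weaker than a written clause.
- **Deaths remain visible.** Deaths before EOT are failures in the ITT analysis at EOT, and all-cause mortality at 15 and 30 days is reported in ITT. This stands and limits the harm.
- **The counts are assumed.** This also stands. The documents give no rate of death on treatment.

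A reader might go further and infer that all deaths on treatment are certainly removed, or that the lower dose threshold for failures is defeated. The documents support neither. Some deaths could be kept as described above, and others fail the dosing minimum anyway. Living early failures with a timely EOT Visit still benefit from the lower threshold.

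**Conclusion.** The point holds as a gap in the wording of SAP 6.1.4.5. Taken literally, the CE-EOT timing bullet excludes a subject with adequate doses who died before an EOT Visit, although both documents give that subject a definite outcome of failure. ME-EOT inherits the exclusion, while CE-PTE could count the same death if an EOT Clinical Failure was recorded.

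The consequence is small. SAP 9.4 says of these additional analyses that intervals are descriptive and no non-inferiority conclusion is drawn. It would be wrong to infer a threat to the trial's conclusions: ECR in ITT, the PTE analyses in ITT and CE, and the stated power do not use CE-EOT.

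The illustrative range is +0.3 to +2.7 points in one arm for 1 to 8 dropped deaths. It assumes 268 evaluable subjects per arm and 89% success, both borrowed from the PTE planning, and that every death meets the other CE criteria and is actually dropped. Bias in the difference needs an imbalance; equal deaths with equal successes produce none. ME-EOT was not calculated separately.

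**What to change.** In SAP 6.1.4.5, add to the CE-EOT timing bullet: *unless the subject died before the EOT Visit*. State that such subjects count as Clinical Failures in CE-EOT if they meet the evaluable-failure dosing rule in 6.1.4.4 and the other CE criteria. Put the same exception in SAP 7.6, where the window exclusion for CE and ME is repeated. ME-EOT then follows through 6.1.5 without its own edit.

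The change is one clause and its mirror. It needs no new data and takes the decision away from site dating habits and case review. The cost is slightly lower CE-EOT and ME-EOT success rates in any arm with such deaths.
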